5.2.4 Final Study Visit

Final Study Visit (End of Month 6)

- Record VAS, ASES Shoulder, and QuickDASH scores.
- Perform Shoulder Series X-Ray for Research Purposes

CONFIDENTIAL

This material is the property of the NYU School of Medicine and Langone Medical Center. Do not disclose or use except as authorized in writing by the study sponsor

6 Assessment of Safety

6.1 Specification of Safety Parameters

This study presents minimal risks as physical exams and barbotage do not generally present with serious associated risks.

6.1.1 Definition of Adverse Events (AE)

An **adverse event** (AE) is any symptom, sign, illness or experience that develops or worsens in severity during the course of the study. Intercurrent illnesses or injuries should be regarded as adverse events. Abnormal results of diagnostic procedures are considered to be adverse events if the abnormality:

- results in study withdrawal
- is associated with a serious adverse event
- is associated with clinical signs or symptoms
- leads to additional treatment or to further diagnostic tests
- is considered by the investigator to be of clinical significance

6.1.2 Definition of Serious Adverse Events (SAE)

Serious Adverse Event

Adverse events are classified as serious or non-serious. A **serious adverse event** is any AE that is:

- fatal
- life-threatening
- requires or prolongs hospital stay
- results in persistent or significant disability or incapacity
- a congenital anomaly or birth defect
- an important medical event

Important medical events are those that may not be immediately life threatening, but are clearly of major clinical significance. They may jeopardize the subject, and may require intervention to prevent one of the other serious outcomes noted above. For example, drug overdose or abuse, a seizure that did not result in in-patient hospitalization, or intensive treatment of bronchospasm in an emergency department would typically be considered serious.

All adverse events that do not meet any of the criteria for serious should be regarded as **non-serious adverse events**.

6.1.3 Definition of Unanticipated Problems (UP)

Unanticipated Problems Involving Risk to Subjects or Others

Any incident, experience, or outcome that meets all of the following criteria:

- Unexpected in nature, severity, or frequency (i.e. not described in study-related documents such as the IRB-approved protocol or consent form, the investigators brochure, etc)
- Related or possibly related to participation in the research (i.e. possibly related means there is a reasonable possibility that the incident experience, or outcome may have been caused by the procedures involved in the research)
- Suggests that the research places subjects or others at greater risk of harm (including physical, psychological, economic, or social harm).

CONFIDENTIAL

This material is the property of the NYU School of Medicine and Langone Medical Center. Do not disclose or use except as authorized in writing by the study sponsor

6.2 Classification of an Adverse Event

6.2.1 Severity of Event

For AEs not included in the protocol defined grading system, the following guidelines will be used to describe severity.

- **Mild** – Events require minimal or no treatment and do not interfere with the participant's daily activities.
- **Moderate** – Events result in a low level of inconvenience or concern with the therapeutic measures. Moderate events may cause some interference with functioning.
- **Severe** – Events interrupt a participant's usual daily activity and may require systemic drug therapy or other treatment. Severe events are usually potentially life-threatening or incapacitating.

6.2.2 Relationship to Study Intervention

The clinician's assessment of an AE's relationship to study intervention is part of the documentation process, but it is not a factor in determining what is or is not reported in the study. If there is any doubt as to whether a clinical observation is an AE, the event should be reported. All AEs must have their relationship to study intervention assessed. In a clinical trial, the study intervention must always be suspect. To help assess, the following guidelines are used.

- **Related** – *The AE is known to occur with the study intervention, there is a reasonable possibility that the study intervention caused the AE, or there is a temporal relationship between the study intervention and event. Reasonable possibility means that there is evidence to suggest a causal relationship between the study intervention and the AE.*
- **Not Related** – *There is not a reasonable possibility that the administration of the study intervention caused the event, there is no temporal relationship between the study intervention and event onset, or an alternate etiology has been established.*

6.2.3 Expectedness

[name] will be responsible for determining whether an AE is expected or unexpected. An AE will be considered unexpected if the nature, severity, or frequency of the event is not consistent with the risk information previously described for the study intervention.

6.3 Time Period and Frequency for Event Assessment and Follow-Up

The occurrence of an AE or SAE may come to the attention of study personnel during study visits and interviews of a study participant presenting for medical care, or upon review by a study monitor. All AEs including local and systemic reactions not meeting the criteria for SAEs will be captured on the appropriate RF. Information to be collected includes event description, time of onset, clinician's assessment of severity, relationship to study intervention (assessed only by those with the training and authority to make a diagnosis), and time of resolution/stabilization of the event. All AEs occurring while on study must be documented appropriately regardless of relationship. All AEs will be followed to adequate resolution.

Any medical condition that is present at the time that the participant is screened will be considered as baseline and not reported as an AE. However, if the study participant's condition deteriorates at any time during the study, it will be recorded as an AE. UPs will be recorded in the data collection system throughout the study.

Changes in the severity of an AE will be documented to allow an assessment of the duration of the event at each level of severity to be performed. AEs characterized as intermittent require documentation of onset and duration of each episode.

CONFIDENTIAL

This material is the property of the NYU School of Medicine and Langone Medical Center. Do not disclose or use except as authorized in writing by the study sponsor

The PI will record all reportable events with start dates occurring any time after informed consent is obtained until 7 (for non-serious AEs) or 30 days (for SAEs) after the last day of study participation. At each study visit, the investigator will inquire about the occurrence of AE/SAEs since the last visit. Events will be followed for outcome information until resolution or stabilization.

All unresolved adverse events should be followed by the investigator until the events are resolved, the subject is lost to follow-up, or the adverse event is otherwise explained. At the last scheduled visit, the investigator should instruct each subject to report any subsequent event(s) that the subject, or the subject's personal physician, believes might reasonably be related to participation in this study. The investigator should notify the study sponsor of any death or adverse event occurring at any time after a subject has discontinued or terminated study participation that may reasonably be related to this study.

6.4 Reporting Procedures – Notifying the IRB

6.4.1 Adverse Event Reporting

Information about any breach of confidentiality will be documented in the electronic data collection system and/or on the paper CRFs, as appropriate. It will be the responsibility of the Principal Investigator to report any Serious Adverse Event (SAE) that occurs during the course of the retrospective data collection to the Institutional Review Board (IRB) within the timeframe specified by NYU SoM.

6.4.2 Unanticipated Problem Reporting

Incidents or events that meet the OHRP criteria for UPs require the creation and completion of an UP report form. It is the site investigator's responsibility to report UPs to their IRB and to the DCC/study sponsor. The UP report will include the following information:

- Protocol identifying information: protocol title and number, PI's name, and the IRB project number;
- A detailed description of the event, incident, experience, or outcome;
- An explanation of the basis for determining that the event, incident, experience, or outcome represents an UP;
- A description of any changes to the protocol or other corrective actions that have been taken or are proposed in response to the UP.

To satisfy the requirement for prompt reporting, UPs will be reported using the following timeline:

- UPs that are SAEs will be reported to the IRB and to the DCC/study sponsor within 1 week of the investigator becoming aware of the event.
- Any other UP will be reported to the IRB and to the DCC/study sponsor within 2 weeks of the investigator becoming aware of the problem.
- All UPs should be reported to appropriate institutional officials (as required by an institution's written reporting procedures), the supporting agency head (or designee), and OHRP within 1 month of the IRB's receipt of the report of the problem from the investigator.

7 Data Monitoring

Data monitoring will be done by [name], the principal investigator. Data monitoring reviews will be conducted quarterly.

He will monitor:

1. Incidents of severe adverse effects (infection, bursitis, fainting or feeling of faintness)
2. Collection and storage of study data was performed as defined in the informed consent form and protocol
3. The risk/benefit to patients has remained the same throughout the course of the study.

CONFIDENTIAL

This material is the property of the NYU School of Medicine and Langone Medical Center. Do not disclose or use except as authorized in writing by the study sponsor

4. If there is a greater than 10 percent difference in frequency of risks between the two study groups, the study will be stopped.

8 Statistical Considerations

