and cortisone/saline (sham) injection will occur concurrently by a different physician from the PI, blinding the PI and patients. The study team members responsible for randomization will converse with the [name], who will be in charge of performing the barbotage and cortisone/saline (sham) procedure. The associated research members and the physician performing the barbotage excluding the PI and patients are the only individuals who will be aware of the blind. Blinding will be maintained until a patient experiences adverse effects, in which case the researchers will inform the primary physician.

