8.2 Measures to Minimize Bias

8.2.1 Enrollment/Randomization/Masking Procedures

Patients will be randomized (1:1) using REDCap. The physicians and patients will be blinded to their assigned treatment group.

As each patient receives the barbotage, the patient nor the PI will not know if they are receiving the cortisone in addition to the barbotage. Study team members and [name] will not be blinded and in position to randomize the patients. [name] will not be blinded to the study as she is performing the procedures. [name], the PI, and his patients will be blinded from which combination of the two they receive (barbotage and cortisone or saline/sham).

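### The section 7 stopping rule at a 10 percent between-arm difference leaves its scale, minimum n, event set and consequence unstated, so one or two events can trigger it, and it gives the arm comparison to a blinded PI

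*Combined protocol and SAP*

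**What the plan says.** Section 7 (Data Monitoring) names one monitor: "Data monitoring will be done by [name], the principal investigator". It adds: "Data monitoring reviews will be conducted quarterly". Of the four things to be monitored, item 1 is "Incidents of severe adverse effects (infection, bursitis, fainting or feeling of faintness"), and item 4 is the stopping rule: "If there is a greater than 10 percent difference in frequency of risks between the two study groups, the study will be stopped". Item 4 does not refer back to item 1.

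Four other places bear on the rule:

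- **Section 6.2.1** defines severity and says: "Severe events are usually potentially life-threatening or incapacitating".
- **Section 4.7.3** separates temporary suspension from premature termination, makes both discretionary, and lets the study resume once concerns are resolved. It does not mention the 10 percent rule.
- **Section 5.1** says that the research members and "the physician performing the barbotage excluding the PI and patients are the only individuals who will be aware of the blind". It also says: "Blinding will be maintained until a patient experiences adverse effects, in which case the researchers will inform the primary physician". **Section 8.2.1** says that "the PI, and his patients will be blinded from which combination of the two they receive".
- **Section 8.2.2** breaks the blind for a single patient, but its trigger is severe adverse events, which is narrower than the trigger in section 5.1.

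**The concern.** The rule is mandatory, yet four things needed to apply it are missing: the scale, the smallest number of patients at which it operates, the events counted, and what follows a crossing. A mandatory rule read at every quarter from the first will meet very small arms, where one or two events make a difference above 10 points. A trial of equally safe arms could then be halted by chance, or the reviewer would have to improvise an interpretation after seeing the data.

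The event set is also unsettled inside section 7. Item 1 calls its events severe but includes a feeling of faintness, which sits badly with the severity definition in section 6.2.1.

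Separately, a between-arm comparison is assigned to someone whom two other sections describe as blinded. Under section 6.3 that person also records the reportable events on which the rule acts.

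**Working it through.** **Plan's own figure.** The documents give no false-stop probability or other operating characteristic for this rule, so there is nothing to reproduce.

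**Inputs from the documents.** 140 patients randomised 1:1, so 70 per arm; quarterly reviews; enrolment estimated at 24 months and study duration also at 24 months (Protocol Summary); 6 months of follow-up.

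**Assumptions.** Equal true event risk in both arms of 1, 2, 5, 10 or 20%; one pooled event endpoint; even accrual; balanced arms; events known at once. Accrual takes 24 months, or 18 months if follow-up must fit inside the stated duration (24 − 6).

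**Step 1: the scale changes the decision.** Take 1/12 v 0/12. The absolute difference is 8.3 points, so no stop. Relative to the larger rate it is 100%, so stop. On a relative reading, one event against none crosses at any n.

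**Step 2: events needed on the absolute reading.** The smallest excess k with k/n > 0.10 is floor(n/10) + 1: 1 event at 9 per arm (1/9 = 11.1%), 2 at 10 to 19, 3 at 20 to 29, and 8 at 70.

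**Step 3: first review.** Over 24 months, 140 × 3/24 = 17.5 patients are enrolled by month 3, about 9 per arm. Any inequality of counts then crosses, so P(cross) = 1 − Σ P(k)², where P(k) is binomial(9, p). At p = 1%: P(0) = 0.99⁹ = 0.9135 and P(1) = 9 × 0.01 × 0.99⁸ = 0.0830. The squares sum to 0.8345 + 0.0069 = 0.8414 (later terms negligible), giving 0.159. At 2% the result is 0.281. Over 18 months, 140 × 3/18 = 23.3, about 12 per arm, and two excess events are needed.

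**Step 4: cumulative chance over all quarterly reviews**, by exact recursion for the first three rows and simulation for the others.

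| Absolute reading | 1% | 2% | 5% | 10% | 20% |
|---|---|---|---|---|---|
| 24-month accrual, first look 9 v 9 | 16 | 30 | 57 | 78 | 90 |
| 24-month, first look 10 v 10 | 2.5 | 8 | 28 | 53 | 75 |
| 18-month, first look 12 v 12 | 1 | 4.5 | 20 | 44 | 67 |
| 24-month, 9 v 9, 6-week event lag, all enrolled in denominator | 9 | 18 | 42 | 67 | 86 |
| 18-month, 6-week event lag, all enrolled in denominator | 0.4 | 1.7 | 11 | 32 | 57.5 |
| 18-month, 6-week lag, only followed patients in denominator (first comparison 6 v 6) | 12 | 23 | 51 | 74 | 88 |

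Entries are percentages.

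**Step 5: where it comes from.** At 5% risk on the first row, 51 of the 57 points accrue at the first review. A single comparison at 70 per arm would cross with probability 0.4, 3.4 and 11.2% at risks of 5, 10 and 20%. As illustration only, applying the rule from 20 per arm takes the first row to about 0.4/2/12.5/31/51%.

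**Step 6: how little a crossing says.** At 1/9 v 0/9 the exact 95% CI for the difference is about −21 to +46 points (Fisher p = 1.0). At 2/12 v 0/12, which also crosses, it is about −11 to +46.5 (p = 0.48).

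**Step 7: blinding, side by side.** Section 7 gives the PI the comparison between groups. Section 5.1 excludes the PI from those aware of allocation, and section 8.2.1 calls the PI blinded. Section 7 describes neither a coded report nor another preparer. Section 8.2.2 unblinds patients with severe events; section 5.1 appears to do so for any adverse effect. What section 7 adds is therefore mainly the routine arm-level tally, plus non-severe events if those count and the narrower trigger applies.

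**The case against.** Several objections carry weight.

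- **The event set.** A reader might infer that the plan gives no idea which events count. That goes too far: item 1 of the same list names a plausible set. What stands is that item 4 is not tied to it and that its use of severe does not fit section 6.2.1.
- **Blinding.** A reader might infer that section 7 by itself unblinds the PI to the trial. The documents do not support that. Individual unblinding is already provided for, unblinded staff exist under section 8.2.1, and the text does not rule out masked labels. What stands is that no masking is provided for and that the two unblinding triggers differ.
- **Bias in the pain endpoint.** This might also be inferred and is not supported: the VAS is completed by patients, who are meant to stay blinded.
- **Size.** The 16 to 30% figures require a first look at 9 v 9 with no lag, and every figure rests on assumed event rates. This is correct. Section 6.1 describes minimal risk, which makes the low rates more natural without fixing them.
- **Direction.** Over-triggering is the cautious error, and section 4.7.3 permits resumption. That is fair, but section 7 does not say that a crossing is only a pause.
- **The relative reading** is the less natural one. The plan should still exclude it in words, because it would react to any lone event.
- **Oversight.** Replacing the PI as recipient would be more than a wording change. This stands and limits the fix.

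**Conclusion.** The point holds in this form. As written, the section 7 rule cannot be applied without choices that the protocol does not make, and on the absolute reading it can halt a trial of equally safe arms on one or two events. The size cannot be stated as a single number. At an assumed 1 to 2% risk the false-stop chance runs from 0.4 to 1.7% (18-month accrual with lag, all enrolled in the denominator) to 16 to 30% (24-month accrual, first look 9 v 9), and it rises steeply if common minor events count. Early reviews cause most of it. It would be wrong to conclude that the trial has a 16 to 30% chance of wrongful termination: the event rate, accrual and look timing are assumptions, and a crossing may mean only suspension.

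The gaps in the rule and the unreconciled PI role rest on the text alone and need no simulation. This should be fixed, but it does not threaten the primary comparison.

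**What to change.** 1. **Reconcile section 7 with sections 5.1, 8.2.1 and 8.2.2.** Have study-team members already unblinded under section 8.2.1 prepare the between-arm table. Apart from individual unblinding, the PI sees pooled or masked-label data. Reconcile the differing unblinding triggers in sections 5.1 and 8.2.2. Who acts on an unmasked table is for the sponsor and IRB.
2. **Complete item 4.** State that the comparison is of the item 1 events, with severe reconciled with section 6.2.1; whether 10 percent is absolute or relative; whether a minimum number per arm applies; and whether a crossing means suspension and review under section 4.7.3 or termination.
3. **Report uncertainty.** Show the exact 95% CI for the risk difference beside each comparison. State the false-stop probability of whatever rule is kept, for the planned accrual, review dates and randomisation method, so that a one- or two-event imbalance is not read as a real difference.

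The threshold, any minimum n and the action on crossing stay with the sponsor and IRB.

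The cost is protocol wording, one calculation, and a short quarterly table from staff who are already unblinded. A minimum n, if chosen, could delay the response to a real early imbalance, and that trade-off should be recorded.

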8.1 Sample Size

We will aim to enroll a total of 140 subjects. According to a post hoc power analysis calculating the effect size using our preliminary data, >128 patients are required with $d=0.6$ to obtain a power of 0.80 and an alpha value of 0.05. Therefore we are including an additional 10 patients per group to account for patients that may be lost to follow up. Statistical analysis will be performed using chi-squared and/or fisher's exact testing depending on size for binary variables. Continuous variables will be compared with paired t-tests if the data is approximately normally distributed. If the data is not normally distributed, Mann-Whitney tests will be used. All protected health information will be removed prior to statistical analysis.

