14	CONFLICT OF INTEREST POLICY	15
15	REFERENCES	17
16	ATTACHMENTS	17

CONFIDENTIAL

This material is the property of the NYU School of Medicine and Langone Medical Center. Do not disclose or use except as authorized in writing by the study sponsor

List of Abbreviations

AE	Adverse Event/Adverse Experience
CFR	Code of Federal Regulations
CRF	Case Report Form
CSOC	Clinical Study Oversight Committee
DCC	Data Coordinating Center
DHHS	Department of Health and Human Services
DSMB	Data and Safety Monitoring Board
FFR	Federal Financial Report
FWA	Federalwide Assurance
GCP	Good Clinical Practice
HIPAA	Health Insurance Portability and Accountability Act
ICF	Informed Consent Form
IRB	Institutional Review Board
ISM	Independent Safety Monitor
MOP	Manual of Procedures
N	Number (typically refers to participants)
NIH	National Institutes of Health
OHRP	Office for Human Research Protections
OHSR	Office of Human Subjects Research
PI	Principal Investigator
QA	Quality Assurance
QC	Quality Control
SAE	Serious Adverse Event/Serious Adverse Experience
SOP	Standard Operating Procedure
US	United States

CONFIDENTIAL

This material is the property of the NYU School of Medicine and Langone Medical Center. Do not disclose or use except as authorized in writing by the study sponsor

Protocol Summary

[figure not shown]
Title	Calcific Tendonitis Treatment-Barbotage vs. Barbotage with Cortisone Injection: A Randomized Controlled Double-Blind Study
Short Title	Calcific Tendonitis Treatment-Barbotage vs. Barbotage with Cortisone Injection
Protocol Number	S19-01299
Population	A sample size of 140 patients belonging to NYU Langone Health with calcific tendonitis will be enrolled including both genders, ages 18-90.
Objectives	The purpose of this study is to determine the efficacy of barbotage therapy by comparing the clinical and sonographic changes in patients that solely receive barbotage to patients receiving the standard of care, barbotage with cortisone injection.
Study Center(s)	Single-center, prospective study
Number of Subjects	We will aim to enroll a total of 140 subjects.
Study Duration	The estimated duration of the study is 24 months.
Subject Participation Duration	Each patient will be present for the day of treatment and follow-up at: 6 weeks, 3 months, and 6 months. Patients will be in the study for 6 months.
Estimated Time to Complete Enrollment	The estimated time to completion of enrollment is 24 months.

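### The sample-size statement in section 8.1 does not reproduce: d = 0.6 needs 90 patients, not more than 128, and 128 plus 10 per group is 148, not 140

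*Combined protocol and SAP*

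**What the plan says.** Section 8.1 (Sample Size) is the only place where the size of the trial is justified. It takes an effect size from a post hoc analysis of preliminary data and concludes that ">128 patients are required with $d=0.6$ to obtain a power of 0.80 and an alpha value of 0.05". For losses it continues: "we are including an additional 10 patients per group to account for patients that may be lost to follow up". The total is given in the same section, and again in the Protocol Summary: "We will aim to enroll a total of 140 subjects". Section 4.6 repeats 140 as an approximate figure.

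Section 8.2.1 gives 1:1 allocation. Section 8.1 does not say whether alpha is one- or two-sided, which outcome d refers to, or what mean difference and SD lie behind it. No multiplicity adjustment appears in the document.

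**The concern.** A standardised difference of 0.6 is moderately large, and 128 is the familiar total for 0.5, so the pairing in section 8.1 looks wrong at once. The loss allowance also fails as plain addition, with no statistical assumption involved.

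The stake is how the result will be read. Section 1.2 says it is unknown whether barbotage alone achieves the same resolution as barbotage with cortisone. A finding of no significant difference is therefore a real possibility, and its meaning depends on what difference the trial could detect. As written, a reader cannot tell whether the trial was sized for 0.5 or 0.6 SD, or how much power it has for either.

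**Working it through.** **Inputs**

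- Alpha 0.05, power 0.80, d = 0.6 (section 8.1). Because d is standardised, SD = 1.
- Allocation 1:1 (section 8.2.1).
- Loss allowance 10 per group, so 2 × 10 = 20 (section 8.1).
- Enrolment 140, so 70 per arm (section 8.1, Protocol Summary).
- Assumption: two-sided alpha. One-sided is also tried below.

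**Step 1: the plan's figure of more than 128 at d = 0.6**

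Normal approximation, per arm: n = 2(z₀.₉₇₅ + z₀.₈₀)² / d².

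- d = 0.6: 2 × (1.960 + 0.842)² / 0.36 = 15.70 / 0.36 = 43.6, so 44 per arm, 88 in total.
- d = 0.5: 15.70 / 0.25 = 62.8, so 63 per arm, 126 in total.

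The exact calculation (two-sample t-test, noncentral t) gives:

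- d = 0.6: 44.6, so 45 per arm, **90 in total**.
- d = 0.5: 63.8, so 64 per arm, **128 in total**.

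The plan's figure is not reproduced at d = 0.6 and is reproduced exactly at d = 0.5. The excess is (128 − 90) / 90 = 42%, too large for rounding.

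**Step 2: other readings of d = 0.6 at alpha 0.05 and power 0.80**

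| Reading | Required |
|---|---|
| One-sided two-sample t | 35.04, so 36 per arm, 72 total |
| Paired t-test (named in section 8.1) | 23.8, so 24 pairs |
| Mann-Whitney, relative efficiency 0.955 | 44.6 / 0.955 = 46.7, so 47 per arm, 94 total |
| Mann-Whitney, worst-case efficiency 0.864 | 44.6 / 0.864 = 51.6, so 52 per arm, 104 total |
| Two-group ANOVA (named in the Protocol Summary), f = d/2 = 0.3 | 89.2, so 90 total |

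None reaches 128. Raising power to 0.90 (two-sided t) gives 59.4, so 60 per arm, 120 in total.

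**Step 3: the loss allowance**

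- Forward: 128 + 20 = 148, which is 8 above 140.
- Backward: 140 − 20 = 120, which is below the stated minimum.

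**Step 4: what the trial delivers** (exact t, two-sided alpha 0.05)

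| Evaluable | Power at d = 0.6 | Power at d = 0.5 | d detectable with 80% power |
|---|---|---|---|
| 120 (60 per arm) | 90.3% | 77.5% | 0.516 |
| 128 (64 per arm) | 92.0% | 80.1% | 0.499 |
| 140 (70 per arm) | 94.1% | 83.6% | 0.477 |

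The normal approximation agrees for the detectable effect at 120: 2.802 × √(4/120) = 0.511.

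**The case against.** **The practical effect is small.** At d = 0.6 the trial has more power than claimed. At d = 0.5 the worst shortfall is 80 − 77.5 = 2.5 percentage points, and only if all 20 budgeted losses occur. This is correct and bounds the harm. It does not make the statement right: either the effect size or the power is misreported.

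**Withdrawals are replaced.** Section 4.7.2 provides for enrolling another patient when one withdraws, so 120 is a floor and not the expected number analysed. That stands, and 120 to 140 is the fair range. But section 8.1 budgets separately for loss to follow-up, which section 4.7.2 does not expressly cover, and replacement does not change the addition.

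**A multiplicity adjustment could explain 128.** Section 2.1 lists four measures. With alpha 0.05/4 = 0.0125, d = 0.6 does need 64 per arm, 128 in total. The true source of 128 is therefore unknown, and d = 0.5 is only the likeliest one. But section 8.1 states "an alpha value of 0.05" and no adjustment is planned. If this was the basis, the stated alpha is wrong instead, and 148 against 140 remains.

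**Perhaps 10 in total was meant.** That gives 138, close to an approximate 140, but the text specifies 10 in each group.

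**Conclusion.** The concern holds on both counts. With the inputs in section 8.1, 90 patients are required, not more than 128 (two-sided exact t; 88 by the normal approximation, 72 if one-sided). Separately, the loss allowance leads to 148, not 140.

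The consequence is a misstated design basis, not a demonstrated lack of power. If d = 0.6 is the target, true power is higher than stated. If d = 0.5 is the target, the stated 80% is missed when all 20 allowed losses occur and met when none do. The documents do not show which of d, the required number or the total is the wrong figure. The power figures assume a two-sided comparison of two independent arms on a single outcome at alpha 0.05.

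This must be corrected, because it is the trial's only sample-size justification and its figures contradict one another.

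**What to change.** Delete the sentence pairing d = 0.6 with more than 128 patients and 80% power. The sponsor should confirm d from its preliminary data, not pick the value that happens to fit 140, and then use one of these statements:

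- **If d = 0.5:** with two-sided alpha 0.05, 64 per arm give 80% power. Enrolling 140 and losing up to 10 per arm leaves 60 to 70 evaluable per arm, with power of 77.5% to 83.6%; at 60 per arm, 80% power applies to d = 0.52.
- **If d = 0.6:** with two-sided alpha 0.05, 60 evaluable per arm give 90% power. Adding 10 per arm for losses gives 70 per arm, 140 in total. Here the figures agree exactly.

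In either case, state sidedness, name the outcome to which d applies, and give the mean difference and SD behind it. If a multiplicity-adjusted alpha was the real basis, state it and carry it into the analysis section.

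The cost is protocol wording only. Enrolment stays at 140 and no procedure changes. Under d = 0.5, guaranteeing 128 evaluable after 20 losses would instead need 148 enrolled, 8 more than planned; that is optional if the lower power is stated openly.
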